10.2 Protocol Deviations

Population: SAF analysis set

10.2.1 Important Protocol Deviations

Important protocol deviations will be summarized in a table on the safety population, by dose level and overall:

- The number of participants with at least one important protocol deviation
- The number of participants with deviation of inclusion/exclusion criteria, overall and by criteria using the information provided in “Study Entry” eCRF page
- The number of participants with deviation of post inclusion criteria, overall and by criteria.

The following listings of important protocol deviations will be provided on the safety population, including:

- Deviations from inclusion or exclusion criteria, using information provided in “Study Entry” eCRF page. This listing will include: dose level, subject identification number, inclusion/exclusion criteria not met and date of deviation.
- Important protocol deviations. This listing will include: dose level, subject identification number, date of protocol deviation, deviation category, deviation description and if the PD occurred after pandemic start.
- A subject listing of any COVID-19 related PD will also be provided.

10.2.2 Reasons Leading to the Exclusion from an Analysis Population

Participants excluded from the DE analysis set will be displayed in a listing. This listing will include: dose level, subject identification number, reason for exclusion from the DE Analysis Set. Reason for exclusion could be:

- Insufficient exposure to peposertib
- Insufficient exposure to RT
- Insufficient exposure to capecitabine
- DLT period not completed.

11 Demographics and Other Baseline Characteristics

Population: SAF analysis set

11.1 Demographics

The following demographic characteristics will be summarized using the information from the “Demographics” eCRF pages.

- Sex: male, female
- Race: White, Black or African American, Asian, American Indian or Alaska Native, Native Hawaiian or other Pacific Islander, Not collected at this site, Other
- Ethnicity: Hispanic or Latino, Not Hispanic or Latino
- Age (years)
- Age categories:
 - < 65 years
 - < 50
 - 50-64
 - ≥ 65 years
 - 65-74
 - 75-84
 - ≥ 85

Specifications for computation:

Age [years]: (date of given informed consent - date of birth + 1) / 365.25

- In case of missing day for at least one date, but month and year available for both dates:
For the derivation of age, the day of informed consent and the day of birth will be set to 1 and the formula above will be used
- In case of missing month for at least one date, but year available for both dates:
For the derivation of age, the day and the month of informed consent and the day and month of birth will be set to 1 and the formula above will be used.

The integer part of the calculated age will be presented.

Data will also be provided in listings (see Section 11.3).

11.2 Medical History

Population: SAF analysis set

The medical history will be summarized from the “Medical History” eCRF page, using the most recent available version of MedDRA (version 21.0 or later) preferred term (PT) as event category and MedDRA system organ class (SOC) body term as Body System category. Each participant will be counted only once within each PT or SOC.

Medical history will be displayed in terms of frequency tables: ordered by primary SOC and PT in alphabetic order.

A supportive listing of medical history data by subject will include all the relevant data fields as collected on the “Medical History” eCRF pages.

11.3 Other Baseline Characteristics

Population: SAF Analysis Set

The following baseline characteristics will be summarized using the information from the “Vital Signs” and “ECOG performance status” eCRF pages.

- Height (cm)
- Weight (kg)
- BSA (m^2) = $([Height(cm) \times Weight(kg)]/3600)^{1/2}$ (Mosteller,1987)
- ECOG Performance status

A listing of baseline characteristics will include the following information (as applicable): Dose level, subject identification number, date of birth, age (years), sex, race, height (cm), weight (kg), BSA (m^2), ECOG performance status and result from pregnancy test (serum β -HCG).

Disease history will be summarized by dose level and overall, in a frequency table including the following information from the ‘DISEASE HISTORY’ eCRF page:

- Disease stage at diagnosis, by stage
- Disease stage at study entry, by stage
- Histopathological classification, by classification.
- TNM classification: each T, N, M category and the TNM classification will be described (TX, T0, N1, etc.)
- MRI-EMVI score
- MRI-CRM score

In addition, a supportive listing of disease history will be provided including the following information from the ‘DISEASE HISTORY’ eCRF page: Dose level, subject identification

number, site of primary tumor, sub site of primary tumor, date of initial cancer diagnosis, histopathological classification, stage at initial diagnosis, stage at study entry, TNM at initial diagnosis and at study entry, MRI-EMVI score at initial diagnosis and at study entry and MRI-CRM score at initial diagnosis and at study entry.

Prior induction therapy details will be displayed in a listing including the following information from the ‘PRIOR INDUCTION THERAPIES’ and ‘PRIOR INDUCTION THERAPY DETAILS’ eCRF pages: Dose level, subject identification number, prior induction therapy (Yes/No), regimen name, overall response, documented progression disease date, Drug(s) given as part of the therapy, start and end dates.

Finally, a listing of the pharmacogenomics findings will include the following information regarding the molecular diagnosis for each participant: Dose level, subject identification number and all relevant information from the “Molecular Diagnosis” section of the “Disease History” eCRF page.

12

Previous or Concomitant Medications/Procedures

Population: SAF analysis set

12.1

Prior Anti-Cancer Treatments and Procedures

The prior anti-cancer treatments and procedures are collected under the “Prior anti-cancer drug therapies”, “Prior anti-cancer surgeries”, and “Prior anti-cancer radiotherapy” eCRF pages.

The listings of prior anti-cancer treatments and procedures will be provided:

- Listing of prior anticancer drug therapies,
- Listing of prior anticancer surgeries,
- Listing of prior anticancer RT.

These will include the subject identification number, dose level and all the relevant collected data-fields on the corresponding eCRF pages.

In addition, a summary table will be provided by dose level and overall, with;

- The number of participants having received prior anti-cancer drug therapies, overall and by type of therapy
- The number of participants having received prior anti-cancer surgeries, overall and by intent (curative intent or not)
- The number of participants having received prior anti-cancer RT.

12.2

Previous and Concomitant Medications

Concomitant medications are medications other than study medications and premedications for study drug, which started prior to first dose date of study treatment and continued during the on treatment period as well as those started during the on treatment period. Previous medications are medications, other than study medications and pre medications for study drug, which started before first dose date of study treatment. A medication may be classified as both concomitant and previous.

In case the date values will not allow unequivocal allocation of a medication to previous/concomitant medication, the medication will be considered as both, previous and concomitant medication (see Section 0 for incomplete or missing dates).

Previous and concomitant medications will be summarized separately based on the “Relevant previous medications” and “Concomitant medications” eCRF pages. The anatomical therapeutic chemical (ATC)-second level and PT will be tabulated as given from the World Health Organization Drug Dictionary (most recent available version of WHO-DD). If multiple ATC can be assigned to a drug, all ATCs will be reported.

Previous and concomitant medications will also be listed. The listings will include: dose level, subject identification number and all corresponding collected data-fields on the corresponding eCRF page.

12.3

Concomitant Procedures

Concomitant procedures are procedures other than study medications and pre medications for study drug, which started prior to first dose date of study treatment and continued during the on treatment period as well as those started during the on treatment period. These will be listed according to the CRF page “Concomitant Procedures”. Procedures started after the on treatment period will be presented and flagged in listing.

In case the date values will not allow unequivocal allocation of a procedure to concomitant procedure, the procedure will be considered as concomitant procedure (see Section 0 for incomplete or missing dates).

The listing will include: dose level, subject identification number and all collected data-fields on the corresponding eCRF page.

12.4

Subsequent Anti-cancer Treatment

Subsequent anti-cancer treatments will be listed according to eCRF pages “Anti-cancer treatment after discontinuation”, “Surgery after discontinuation” and “Anti-cancer radiotherapies after discontinuation”. The listings will include: dose level, subject identification number and all collected data-fields on the corresponding eCRF pages. Name of the anti-cancer RT will be tabulated as given from the most recent available version of WHO-DD .

In addition, participants who underwent rectal surgery after Week 15 will be listed according to eCRF page “Rectal surgery after Week 15 details”. This listing will include: dose level, subject identification number and all collected data fields on the corresponding eCRF page.

13

Treatment Compliance and Exposure

Population: SAF analysis set

Treatment compliance and exposure will be listed and summarized by dose level and overall using the SAF analysis set.

All dosing calculations and summaries will be based on “M3814 (PEPOSERTIB)/PLACEBO Administration”, “Radiotherapy Administration” and “Capecitabine Administration” eCRF pages.

In the Phase Ib part, participants will be assigned peposertib given in combination with capecitabine 825 mg/m² twice daily 5 days/week. The starting dose of peposertib for the first cohort will be 50 mg once daily 5 days/week. The planned dose of RT to the tumor area is

- 50 Gy with a schedule of 25 days and
- 50.4 Gy with a schedule of 28 days

For the calculations, only doses > 0 will be taken into account if not otherwise specified.

Treatment duration

The duration of peposertib treatment (in weeks) during the study is defined as :

$$\text{duration} = \left(\frac{\text{date of last dose of peposertib} - \text{date of first dose of peposertib} + 1}{7} \right).$$

The durations of RT and capecitabine treatments (in weeks) are derived correspondingly.

Cumulative dose

Cumulative doses will be calculated based on the actual doses received by the participants as filled in the relevant administration eCRF pages.

The cumulative dose (mg) of peposertib will be calculated as the sum of all actual doses that the subject received.

The cumulative dose (Gy) of RT will be calculated as the sum of all actual doses that the subject received (Actual daily Dose PTV1).

The cumulative dose (mg/m²) of capecitabine will be calculated as the sum of the total daily doses that the subject received.

The total daily dose (mg/m²) of capecitabine per subject is the sum of the total dose that the subject received at each fraction day. At a given fraction day, the total daily dose (mg/m²) received is derived as:

$$\text{Total daily dose} = [\text{Actual morning dose administered (mg)} + \text{Actual evening dose administered (mg)}] / \text{BSA (m}^2\text{)}$$

The BSA measured at baseline will be used for all visits, unless the measured weight for a participant varies more than 10% from baseline. The recalculated BSA is derived based on formula described in Section **Error! Reference source not found.**, using weight measured at the corresponding visit. In case the weight measurement is missing, the weight measurement closest to the administration date will be used. If there are two measurements that are equal distance away from the missing measurement, the earliest measurement will be used.

Dose intensity

Dose intensity will be based on the planned dose as defined in the CTP and defined as:

- For peposertib:

$$\text{Dose intensity (mg/weeks)} = \left(\frac{\text{cumulative dose (mg)}}{\text{duration (weeks)}} \right)$$

- For RT:

$$\text{Dose intensity (Gy/weeks)} = \left(\frac{\text{cumulative dose (Gy)}}{\text{duration (weeks)}} \right)$$

- For capecitabine:

$$\text{Dose intensity (mg/m}^2\text{/weeks)} = \left(\frac{\text{cumulative dose (mg/m}^2\text{)}}{\text{duration (weeks)}} \right)$$

Relative dose intensity

Relative dose intensity will be based on the planned dose as defined in the CSP. The relative dose intensity is defined as:

- For peposertib:

$$\text{Relative dose intensity (\%)} = \left(\frac{\text{cumulative dose (mg)}}{x * \text{dose level (mg)}} * 100 \right)$$

- For RT:

$$\text{Relative dose intensity (\%)} = \left(\frac{\text{cumulative dose (Gy)}}{x * \text{planned daily dose (Gy)}} * 100 \right)$$

- For capecitabine:

$$\text{Relative dose intensity (\%)} = \left(\frac{\text{cumulative dose (mg/m}^2\text{)}}{x * \text{planned daily dose (mg/m}^2\text{)}} * 100 \right)$$

Where planned daily dose (mg/m²) is the sum of planned doses per day . Each fraction day, the planned daily dose (mg/m²) is derived as:

$$\text{Planned daily dose} = \text{Planned morning dose (mg/m}^2\text{)} + \text{Planned evening dose (mg/m}^2\text{)}$$

For all 3 relative intensity formula above, x = 25 or 28, depending on the number of fraction doses the participant received.

The relative dose intensity will be displayed using the following categories:

- > 110%
- [80% - 110%]
- [65% - 80%[
- [50% - 65%[
- < 50%

Statistical outputs

The treatment exposure and compliance will be summarized in 4 tables including informations for each study treatment (peposertib /RT/capecitabine).

The first table will summarize the duration in weeks of each treatment (peposertib /RT/Capecitabine), by displaying the number of participants by dose level in each of the following categories:

- < 2 weeks
- [2 - 4 weeks[
- [4 - 6 weeks[

- ≥ 6 weeks

The table will also display summary statistics of the duration in weeks of each treatment.

The second table will summarize the number of total administrations of each treatment (peponsertib /RT/capecitabine), by displaying the number of participants by dose level in each of the following categories:

- < 10 administrations/fraction days (peponsertib /RT)
-]10 -20 administrations/fraction days] (peponsertib /RT)
-]20 - 25 administrations/fraction days] (peponsertib /RT)
-]25 - 28 administrations/fraction days] (peponsertib /RT)
- > 28 administrations/fraction days (peponsertib /RT)

The categories to display for cisplatin are:

- ≤ 20 administrations
-]20 - 40 administrations]
-]40 - 56 administrations]
- > 56 administrations.

The third table will summarize the cumulative dose, dose intensity and relative dose intensity for each treatment.

The fourth table will summarize dose reductions by dose level, with for each treatment (peponsertib /RT/capecitabine):

- Number of participants without any dose reduction
- Number of participants with at least one dose reduction
- Number of participants who did not receive this study intervention
- Number of participants with a minimum of 90%, 70-90%, 50-70%, and < 50% level of the planned dose.

The listing of exposure data (including e.g. start date and time of administration, planned and actual doses, frequency, change in dose and meal time before dose) will be provided by subject as recorded from the related eCRF pages and for each peponsertib, RT and capecitabine administration.

In addition, a summary listing will be provided with the treatment duration in weeks, the total number of treatment administrations/fraction days received, the cumulative dose, and the relative dose intensity for each subject and treatment.

In addition, a listing of all participants receiving peposertib will be displayed to address accountability for peposertib according to page “peposertib/Placebo accountability” of eCRF. This listing will include the subject identification number, and all collected fields of the corresponding eCRF Page.

14 Efficacy Analyses

No primary efficacy endpoints are planned in Phase Ib of this study. Secondary efficacy endpoints include the composite endpoint of pathological complete response / clinical complete response (pCR/cCR), disease-free survival (DFS) time, pCR according to local review, cCR and time to local/distant recurrence.

In the context of efficacy analyses when using ‘surgery’, the rectal surgery at Week 15 is meant. Consequently, delayed rectal surgeries, or surgeries other than the one planned at Week 15 are not considered.

14.1 Secondary Endpoints: pCR, cCR, and pCR/cCR

Population: FAS analysis set

Pathological complete response

Only subjects who undergo surgery at Week 15 can be considered as pathological complete responders. Subjects with pCR will be identified based on the “Histological response” item on the “RECTAL SURGERY AT WEEK 15 DETAILS” eCRF page.

Clinical complete response

Clinical complete response will be assessed according to the tumor evaluation charter. Participants with cCR will be identified based on the “Overall response” item on the “Tumor Assessment (According to NCCN) after RT in ETT/ Week 14” eCRF page.

Composite endpoint of pathological complete response/clinical complete response

[figure not shown]
Participants are considered as responders to the composite endpoint pCR/cCR if 1 of the following 2 criteria is fulfilled (Figure 1):

- Participant had surgery and has pCR (Histological response on “Rectal surgery at week 15 Details” eCRF page is ‘Pathological Complete response (pCR)’)

- Participant did not undergo surgery but has cCR (defined above; Overall Status on “Tumor Assessment (According to NCCN) after RT in ETT/ Week 14” eCRF page is ‘Clinical Response’).

Participants who are not operated and do not undergo the procedures to define cCR or have histological response and pathological response not ‘Complete response’ will be regarded as non-responders for the composite endpoint.

Figure 1 **Derivation of Composite Endpoint**

cCR=Clinical complete response, MRI=Magnetic Resonance Imaging, pCR=Pathological complete response.

Analysis Methods

Table 5 Summary of analyses performed on the composite endpoint of pCR/cCR, pCR and cCR

Analysis (Analysis Population)	Derivation	Statistical Analysis Methods	Missing Data Handling
Secondary endpoint: Composite endpoint of pCR/cCR			
Primary (FAS)	Derivation of the pCR/cCR composite endpoint (pCR based on local review) is described in Section 14.1.	The proportion of participants with pCR/cCR is indicated together with the 95%-Clopper-Pearson CI (Clopper & Pearson, 1934).	Participants who are not operated and do not undergo the procedures to define cCR as per tumor assessment charter or participants who have no pCR and no cCR will be regarded as non-responders
Secondary endpoint: pCR			
Primary (FAS)	The definition of pCR is provided in Section 14.1. pCR will be analyzed once on the local review of the histology slides	The proportion of participants with pCR will be reported together with the corresponding 95% CIs (Clopper & Pearson, 1934)	Participants who are not operated or have Pathological Response = 'No pathological complete response' will be regarded as non-responders
Secondary endpoint: cCR			
Primary (FAS)	The definition of cCR is provided in Section 14.1.	The proportion of participants with cCR will be reported together with the corresponding 95% CIs (Clopper & Pearson, 1934)	Participants who do not undergo the procedures to define cCR per tumor assessment charter, or have clinical response = 'No clinical complete response' will be regarded as non-responders

cCR = clinical Complete Response; CI = Confidence Interval; FAS = Full Analysis Set; pCR = pathological Complete Response

Proportion of responders with the 95%-Clopper-Pearson CI for pCR/cCR as well as for each component of the composite endpoint (subjects with surgery and pCR, subjects without surgery and cCR and subjects with cCR regardless of surgery), will be displayed in a table by dose level and overall. For pCR, a dedicated table will summarize the proportion of participants who had surgery at week 15, as well as the outcome of surgery, and the proportion and 95% Clopper Pearson CI of participants who had pCR. For cCR, a dedicated table will summarize the number who had at least one procedure (Endoscopy, DRE, EUS and/or MRI) performed during the tumor assessment at ETT/Week 14, as well as the overall status of the tumor assessment performed at week 14, the proportion and 95% Clopper Pearson CI of participants with "Complete response" and the results by tumor assessment method.

Additionally all information available on the “TUMOR EVALUATION - WEEK 14” and “TUMOR EVALUATION - WEEK 15” eCRF pages will be described in a table with the following variables:

- MRI-EMVI score
- MRI-CRM score
- ypTNM score
- Surgical-CRM score
- Modified Ryan scheme

All tumor assessments will be displayed in two listings. Tumor assessments at Screening and at Week 14/ETT will be sorted by dose level and subject identification number and listed with the following variables:

- Dose level
- Visit
- Subject identification number
- Method of tumor assessment
- Date of tumor assessment
- Outcome of the tumor assessment

Tumor assessments during the long-term safety and survival follow-up period will be sorted by dose level, subject identification number and assessment visit and listed with the following variables:

- Dose level
- Subject identification number
- Assessment visit
- Date of imaging
- Assessment method
- Overall status.

Finally, all information available on the “RECTAL SURGERY AT WEEK 15” eCRF page will be listed. The listing will be sorted by dose level, subject identification number and date of surgery and will display the following variables:

- Dose level

- Subject identification number
- Date of surgery
- Surgery procedure
- Outcome of surgery
- Histological response.

14.2

Secondary Endpoint: Disease-Free Survival

Population: FAS analysis set

Disease-free survival (DFS) time is defined as the time from the first treatment day to the date of the first documentation of objective progression of disease (PD) or death due to any cause, whichever occurs first. DFS data will be censored on the date of the last adequate tumor assessment for participants who do not have an event (PD or death) or for participants with an event after two or more subsequent missing tumor assessments (i.e. 2 times the scheduled time interval between two subsequent response assessments). Participants who do not have a baseline tumor assessment or who do not have any post baseline tumor assessments will be censored at the start of first trial treatment unless death occurred on or before the time of the second planned tumor assessment, in which case the death will be considered an event.

The last adequate tumor assessment is defined as the last tumor assessment result that is not “NE” or “NA”.

Disease-free survival in months is calculated as follows:

$$\text{DFS (months)} = [\text{date of event or censoring} - \text{treatment start date} + 1]/30.4375$$

Table 6 Date of event / censoring for DFS analysis

Status		Censoring	Date of event / censoring
Progressed or died	No consecutive missing tumor assessments	Event	Minimum (Date of PD, Date of death)
	After two or more subsequent missing tumor assessments (i.e. 2 times the scheduled time interval between two subsequent response assessments)	Censored	Date of last tumor assessment with outcome CR, Nearly-CR or IR or treatment day 1, whatever is later

Neither progressed nor died and no missed tumor assessment	Censored	Date of last tumor assessment with outcome CR, Nearly-CR or IR or treatment day 1 whatever is later
No baseline or no post-baseline tumor assessment and no death within 147 days (21 weeks) of study intervention start	Censored	Treatment day 1
No baseline or no post baseline tumor assessment and death within 147 days (21 weeks) of study intervention start	Event	Date of death

CR = Complete response; IR = Incomplete response; PD = Progressive disease

If more than one condition is met for censoring, the earliest one is considered.

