Physical Examination	X	Physical examination (including body weight) will report findings in the irradiated area during Short- and Long-Term FU periods.
ECOG PS	X	
Adverse Event Assessment	X	Evaluation of ongoing or new AEs assessed as related to study intervention until resolution or permanent outcome. New SAE assessed as unrelated to study intervention only up to Wk 27.
Concomitant Therapy	X	
Adjuvant Chemotherapy	X	Adjuvant chemotherapy if given, according to local guidelines, must start between 1 and 3 mo after surgery.
Hematology	X	
Serum Chemistry and Coagulation	X	

Study Periods	Long-term Safety FU	Notes
Visit Weeks	19 to 52	
Visit Week	21 and 27 wk after start of study intervention/ randomization: Wk 21 and 27; thereafter every 3 mo in Yr 1: Wk 39 and 52	Participants followed-up until 1 year after start of study intervention/randomization, or earlier due to any reason whereby tumor assessments are no longer applicable (e.g. if new treatment is started, study discontinued, withdrawal of consent). Adjuvant chemotherapy is allowed as per local standards (see Section 6.5). Participants receiving adjuvant chemotherapy will continue to follow the schedule of activities as per protocol. If adjuvant chemotherapy is given any additional safety evaluations/laboratory tests will be as per local practice. Reason for early discontinuation should be captured in source documents. If EOT occurs before Wk 52, all assessments must be done as planned for Wk 52.
Visit Windows (Week)	± 1 for Wk 21; ± 2 for other visits	

Participants who have already been followed up for more than 1 year (Long-term Safety or Survival Follow-up) will be discontinued from the study after the approval of protocol amendment version 4.0 by the respective Health Authority and Ethics Boards. Participants will be informed of the discontinuation by the Investigator via a phone call. No further study visits or assessments are planned.

Assessment and Procedures

Carcinoembryonic Antigen	X	
CCI		
MRI/CT	X (starting Wk 27)	T ₂ weighted and diffusion weighted, without gadolinium. No MRI/CT at Wk 21.

AE=adverse event, CT=computerized tomography, ctDNA=circulating tumor DNA, DBP=diastolic blood pressure, ECOG PS=Eastern Cooperative Oncology Group Performance Status, EOT=End of Trial, FU=Follow-up, MRI=magnetic resonance imaging, SAE=serious adverse event, SBP=systolic blood pressure.

CCI

Table 4 Pharmacokinetic Sampling Schedule of Peposertib and Capecitabine

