8.1.2 Tumor Evaluation Methods and Response Assessment

Rectal cancer staging, and measurement at baseline and after chemoradiation should be performed as per NCCN Guidelines for Patients Rectal Cancer 2019. For participants who received induction treatment the baseline assessments will be based on MRI, endoscopy and DRE and biopsy, if required. For participants without induction treatment, the baseline assessment will consist of MRI only. For all participants the assessments after chemoradiation (Week 14) will include MRI, endoscopy and DRE and biopsy, if required. This is all based on a modification of tumor evaluation as described by [Maas 2015](#). Tumor assessments done during long-term Safety Follow-up will only include MRI (T_2 weighted and diffusion weighted) or CT scans ([Table 1](#) and [Table 2](#)).

Baseline assessments are to be taken not earlier than 4 weeks prior to study intervention start/randomization. After study intervention start/randomization, tumor assessments will be performed at 14 weeks (± 7 days) after study intervention start/randomization (i.e. before surgery) and 27 weeks (± 2 week) after study intervention start/randomization, every 3 months thereafter (± 2 weeks) until 1 year after study intervention start/randomization.

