MRI-T2W	Increase in tumor size	
 • More intermediate than dark T2 signal, • no T2 scar AND/OR 
 • No regression of lymph nodes 	
 • Mostly dark T2 signal, • Some remaining intermediate signal AND/OR 
 • Partial regression of lymph nodes 	
 • Normal appearing bowel wall without any fibrosis in the tumor bed. • Only dark T2 signal, no intermediate T2 signal. • No visible lymph nodes or very few, small (< 5 mm nodes)

MRI=magnetic resonance imaging.

All participants, including those not undertaking surgery after chemoradiation are expected to continue loco-regional status evaluation (Table 17, MRI and optional Endoscopy/Digital), until progressive disease, at the frequency described in Section 8.1.2 and the SoA (Table 2) for Long-term Follow-up evaluations (Week 27, thereafter every 3 months in Year 1: Weeks 39 and 52).

Table 17 Response Criteria During Long-Term Safety Evaluation

Method	Progression	Complete Response
MRI-T2W or CT	
 • Local recurrence AND/ OR 
 • distant recurrence 	
 • No evidence of disease

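### SAP 14.2, Table 6: the 147-day limit for counting a death as a DFS event matches no tumor assessment in the current schedule

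*SAP*

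**What the plan says.** SAP 14.2 has a dedicated rule for participants who lack a baseline tumor assessment or any post-baseline one. They are censored at the start of treatment, "unless death occurred on or before the time of the second planned tumor assessment"; in that case the death is an event.

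Table 6 of the same section carries the rule in two rows:

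- Censored at treatment day 1: "No baseline or no post-baseline tumor assessment and no death within 147 days (21 weeks) of study intervention start".
- Event at the date of death: "No baseline or no post baseline tumor assessment and death within 147 days (21 weeks) of study intervention start".

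Table 6 also has general rows for anyone who progressed or died. One gives an event under the condition "No consecutive missing tumor assessments". The other censors after two or more missed assessments, which it defines as twice the scheduled interval. The only tie rule is the footnote: "If more than one condition is met for censoring, the earliest one is considered".

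The schedule comes from the protocol. Section 8.1.2 states: "tumor assessments will be performed at 14 weeks (± 7 days) after study intervention start/randomization (i.e. before surgery) and 27 weeks". Table 2 in section 1.3 adds "No MRI/CT at Wk 21", and Appendix 5 gives the later visits as "Week 27, thereafter every 3 months in Year 1: Weeks 39 and 52". The SAP's modification history says that this SAP version follows protocol version 4.0.

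**The concern.** The text defines the limit by an event in the schedule, and the table defines it by a number of days. The two should give the same date, but Week 21 is not a tumor assessment in the schedule that the SAP follows.

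The text also does not say whether the baseline scan counts as the first planned assessment. Two programmers could therefore classify the same death differently: as an event at the date of death, or as censored at day 1. Censoring at day 1 removes a known death from the DFS estimate.

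**Working it through.** **Inputs.** Planned assessment weeks and windows: protocol 8.1.2, Table 2 and Appendix 5. Limit: SAP Table 6. DFS in months: SAP 14.2, (date − start + 1)/30.4375.

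**1. The plan's figure.** 21 × 7 = 147 days. The conversion is correct.

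**2. The schedule in days.**

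| Planned assessment | Days | Window |
|---|---|---|
| Week 14 | 14 × 7 = 98 | ± 7 days: 91 to 105 |
| Week 27 | 27 × 7 = 189 | ± 14 days: 175 to 203 |
| Week 39 | 39 × 7 = 273 | ± 14 days: 259 to 287 |
| Week 52 | 52 × 7 = 364 | ± 14 days: 350 to 378 |

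No row gives 147, and no window contains it.

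**3. What the text rule gives.**

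- Second post-baseline assessment: Week 27 = 189 days. This is 189 − 147 = 42 days later than the table, or 203 − 147 = 56 days later if the window counts.
- Baseline counted as the first assessment: Week 14 = 98 days. This is 147 − 98 = 49 days earlier than the table.

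**4. The dedicated rule applied to a death with no post-baseline assessment.**

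| Day of death | Table 6, dedicated rows | Text, second post-baseline | Text, baseline counted |
|---|---|---|---|
| up to 98 | event | event | event |
| 99 to 147 | event | event | censored, day 1 |
| 148 to 189 | censored, day 1 | event | censored, day 1 |
| after 189 (nominal) | censored, day 1 | censored, day 1 | censored, day 1 |

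The SAP numbers the day of first treatment as day 1, while Table 6 counts days from the start. The one-day difference does not change the pattern.

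**5. Size for one participant (assumption: death on study day 170).** As an event: 170/30.4375 = 5.59 months. Censored at day 1: 1/30.4375 = 0.03 months.

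**6. Effect on the overall curve (illustration).** Assume 19 participants in the analysis set (the number treated by 06 May 2021), one such death, no other censoring, and k other events earlier than day 170. The 6-month Kaplan-Meier estimate is (18 − k)/19 if the death is an event and (18 − k)/18 if it is censored at day 1.

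- k = 0: 18/19 = 94.7% against 18/18 = 100%, a difference of 5.3 points.
- k = 5: 13/19 = 68.4% against 13/18 = 72.2%, a difference of 3.8 points.

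With no affected participant the difference is 0.

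**The case against.** **Reach.** The rule touches very few people. MRI-evaluable disease is an entry criterion, the Week 14 visit is mandatory, and the protocol synopsis reports 16 of 19 treated participants as followed to Week 19. No hypothesis is tested. All of this stands and keeps the point minor. It does not make the number right.

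**Origin of the number.** The protocol's amendment history records that a Week 21 scan was dropped in version 3.0, which may explain the 147 days. That is history, not an error. But this SAP version declares that it follows version 4.0, and its text does not tie the limit to earlier versions.

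**A stronger reading.** A reader might infer that Table 6 contradicts itself with nothing to settle it: a participant who dies on study day 170 after missing only Week 14 seems to meet both the general event row and the 147-day censoring row. The documents do not support this in full, for two reasons.

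- The sentence in 14.2 is a rule specifically for these participants, so it points away from the general rows. Table 6 merely fails to repeat this.
- The general rows define two missed assessments by twice the scheduled interval, and the SAP does not fix where the count starts. From a screening scan on day −14 to study day 170 is 183 days (there is no day 0), which exceeds 2 × 13 weeks = 182. From day −28 it is 197 days, which exceeds 2 × 14 weeks = 196. On those counts the general rows also censor at day 1. Counted from treatment start, 169 days, they do not.

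What remains is that the footnote ranks censoring conditions only, so the table does not itself state that the dedicated rows displace the general ones.

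**An error of calculation?** A reader might also infer one. There is none; the number and the schedule disagree.

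**Conclusion.** The point holds as a mismatch between the SAP text, SAP Table 6 and the current assessment schedule. The 147-day limit fits neither way of counting the second planned assessment. On the natural post-baseline reading, a known death on days 148 to 189 is an event under the text and censored at day 1 under the table.

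The severity is minor. The documents do not give the number of participants concerned; 0 to 1 is an assumption. The Kaplan-Meier differences illustrate one assumed participant and are not an estimate of bias in the trial. They give no ground for saying that the DFS results are materially distorted.

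**What to change.** Change SAP 14.2 as follows:

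1. In both dedicated rows of Table 6, replace 147 days (21 weeks) by 189 days (27 weeks), and state one choice on whether the + 2-week window is included (203 days).
2. In the text, insert the word post-baseline so that the limit is the second planned post-baseline tumor assessment.
3. Add below Table 6: *For participants with no baseline or no post-baseline tumor assessment, only the two dedicated rows apply; the Progressed or died rows do not.* This also settles the participant with no baseline but documented progression, who is then censored at day 1 unless death falls within the limit, as the 14.2 text already implies.

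Separately, as a label correction that does not enter the censoring rule: SAP section 5 still shows 5 years as the timeframe in the safety, DFS and recurrence rows, while protocol section 3 and SAP 6.4 use 1 year. Change the three labels to 1 year.

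The cost is SAP wording only: two table rows, one word, one sentence and three labels. No new data and no new method are needed.
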